# 11.5 Device Adverse Reporting Failures, Malfunctions and Re-use

All device deficiencies will be recorded on the clinical investigation device deficiency log and where appropriate in the participant's medical records. Device deficiencies which could have caused a SADE must be reported to the device manufacturer (Afferent Medical Solution Ltd) and the Sponsor within 24 hours of becoming aware of the event by submitting a Device Reporting Form to [contact]. Device deficiencies must be recorded and reported throughout the Clinical Investigation. AffeX-CT has been specifically designed to be used by only one patient and must not be re-used by other patients.

# 11.6 Notification and reporting of Serious Adverse Events (SAEs), and Unexpected Serious Adverse Device Events (USADEs)

Refer to Investigator Brochure sections 9.2 and 9.3. AllSAEs that are considered to be 'related' and 'unexpected' are to be reported to the Sponsor and the Sponsor's representative within 24 hours of learning of the event. The SAEs and reportable device deficiencies must be reported from consent until the participant's last follow-up visit. All Serious Adverse Event (SAEs) and Unexpected Serious Adverse Device Events (USADEs) will be recorded in the participants' notes, the CRF, the Sponsor SAE form and reported to the device manufacturer (Afferent Medical Solution Ltd) and the Sponsor (administered by the Joint Research Management Office or agreed representative) (except those specified in this protocol as not requiring reporting). SAE form and reported to the Sponsor (Joint Research Management Office via mailbox at [contact]), Afferent Medical Solution Ltd. ([contact]) within 24 hours of the Chief Investigator or Sub-Investigator(s) becoming aware of the event. Nominated Sub-Investigators (as listed on the Investigator at the participating sites. SAEs and reportable device deficiencies will be reported from consent until the participant's last follow-up visit.

#### 11.7 Sponsor medical assessment

The Sponsor has delegated the responsibility for oversight of investigational device safety profile and medical assessment of safety events to the Chief Investigator as medical assessor The Chief Investigator must review all SAEs and reportable device deficiencies within 72 hours of receipt. This review will encompass seriousness, relatedness, and expectedness. Day 0 for all USADEs is when the USADE is received by the Chief Investigator and / or coordinating team and/ or Sponsor (whichever is first). The CI must also maintain oversite of non-serious AEs reported on the case report forms and review them periodically to confirm agreement. It is expected that the Chief Investigator will achieve oversight of AffeX-CT device safety profile through the trial committees as per section 25.0 of the CIP.

# 11.8 Procedures for reporting blinded USADEs

The Chief Investigator, as Sponsor medical assessor, will assess the event blinded for all possible active and placebo AffeX-CT device procedures. The device manufacture's safety teams will be unblind and can submit unblind safety reports to the MHRA as required.

#### 11.9 Urgent Safety Measures

The Chief Investigator may take urgent safety measures to ensure the safety and protection of the clinical study participants from any immediate hazard to their health and safety. The measures should be taken immediately. In this instance, the approval of the Competent Authority prior to implementing these safety measures is not required. However, it is the responsibility of the Chief Investigator to attempt, where possible, to discuss the proposed change with the Sponsor and Medical Advisor at the MHRA (via telephone) prior to implementing the change if possible. The Chief Investigator has an obligation to inform both the MHRA and Research Ethics Committee in writing within 3 days of implementing the Urgent Safety Measure. They must also submit a substantial amendment

documenting the changes with 14 days of implementing the urgent safety measure. The Sponsor must be sent a copy of the correspondence with regards to this matter as soon as it is sent.

### 12.0 Annual reporting

Annual Progress Report will be written by the Chief Investigator and submitted to the Sponsor for review prior to submission to the REC. The Annual Progress Report is due within 30 days of the anniversary date of the "favourable opinion" letter from the REC.

# 13.0 Statistical and data analysis

#### 13.1 Sample size calculation

This is a pilot study designed to collect data required to develop a larger efficacy trial. An adjusted sample size of 36 patients is required to have a 90% chance of detecting, as significant at the 5% level, a decrease in the coefficient of variation in systolic blood pressure from 15mmHg in the sham group to 10mmHg in the VAN group [assuming 5% non-compliance rate in each group]. High blood pressure variability (SBP SD ≥16 mm Hg) is associated with at least 20% worse neurological outcome, as judged by failure to achieve modified Rankin Scale 0−2 90 days after mechanical thrombectomy. Power Analysis & Sample Size software (PASS 2022) was used to determine the sample size. The calculated sample size allows for dropout of 5 patients.

#### 13.2 Learning Curve

There is no learning curve consideration to account for. Training for research staff administering the device will be provided with information about the device and will be supervised on the device usage.

#### 13.3 Planned recruitment rate

The estimated planned recruitment rate is ≥2 participants/week. The mechanical thrombectomy service currently treats >25 patients/month. Duration of participant entry is seven days. The study should be completed within five months, with recruitment carefully monitored by the TMG on a weekly basis. Anticipated screen failure rates are minimal as strict criteria are applied for patients to be eligible for mechanical thrombectomy. From our recent study in acute orthopaedic trauma, the anticipated withdrawal rate is<5%. There are no competing/similar studies recruiting the same cohort of potential participants. The proposed start and end date and duration of funding is realistic to ensure the recruitment targets are feasible.

#### 13.4 End of trial definition

The end of trial is defined as the last trial participant completing their seven day visit. The Chief Investigator is delegated the responsibility of submitting the end of trial notification to REC and MHRA once reviewed by the Sponsor. The end of trial notification must be received by the REC and MHRA within 90 days of the end of the study. If the study is ended prematurely, the Chief Investigator will

VANS v3.0 20.04.2023 Page 31 of 44

notify the Sponsor, REC, and MHRA within 15 days, including the reasons for the premature termination.

# 14.0 Statistical Analysis

A full statistical analysis plan will be developed prior to any safety or final analysis. During the recruitment period the statistician will perform a safety analysis if specifically requested by the Trial Steering Committee (TSC). No safety analysis is planned at the outset. This will be outlined accordingly in the TSC charter.

#### 14.1 Summary of baseline data and flow of participants

Baseline characteristics and clinical data for patients randomised to sham and stimulation will be summarised but not subjected to statistical testing. Numbers (%) for categorical variables and means (SD) or medians (IQR) for continuous variables as appropriate will be provided separately for each group. A log will be kept of eligible patients not recruited to the trial. Reasons for non-participation will be categorised and summarised. Participation in the trial, treatment allocation and completeness of follow-up will be illustrated by a CONSORT flow diagram.

Baseline data will be presented for the following factors, separately by randomised trial group:

- Age
- Sex
- Estimated body-mass index
- Medical comorbidities
- Vital signs

# 14.2 Analysis of participant populations

The main analyses of the primary and secondary endpoints will be conducted on an intention-to-treat population, consisting of all participants with available data based on the trial group to which they were randomized to, irrespective of their compliance to their prescribed treatment as specified in the protocol. For continuous endpoints, mean, and SD, and number of participants with available data will be presented along with estimated crude and adjusted mean differences between trial arms. Binary endpoints will be shown as the number with each endpoint and total number in each group along with the percentage. For binary endpoints, the crude and adjusted odds ratios (ORs) will be estimated.

# 14.3 Primary endpoint analysis

The primary outcome - coefficient of variation in systolic blood pressure - will be analysed by repeated measures ANOVA. Significance will be set at p<0.05. Similar analyses of secondary outcomes will be undertaken by intention to treat principle, according to the treatment to which they were randomised.

VANS v3.0 20.04.2023 Page 32 of 44

#### 14.4 Secondary endpoint analysis

Blood pressure and heart rate variability measures will be analysed by repeated measures ANOVA (significance set at p<0.05), analysed in the same way as for the primary endpoint, as detailed above. Specifically, this entails systolic and diastolic blood pressure variability (standard deviation, average real variability, successive variation and residual standard deviation) plus time and frequency domain measures of autonomic cardiac modulation in the first 24 hours after mechanical thrombectomy. The following secondary outcomes will be reported but not subject to statistical testing.

- Blood pressure variability in the first 24 hours from start of mechanical thrombectomy
- Heart rate variability in the first 24 hours from start of mechanical thrombectomy
- NIH Stroke Scale (NIHSS)
- Arrhythmias
- Myocardial injury

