# 2.3.2 Secondary endpoint(s)

- Systolic blood pressure variability from blood pressure measured in each patient during the first 24 hours from the start of mechanical thrombectomy.
- Disatolic blood pressure variability from blood pressure measured in each patient during the first 24 hours from the start of mechanical thrombectomy.
- Heart rate variability measured during each period of transcutaneous autonomic neuromodulation.
- NIH Stroke Scale (NIHSS) measured in each patient before the start of mechanical thrombectomy and 24 hours after the start of procedure.
- Clinically recorded arrhythmias in each patient during the first 24 hours after the start of mechanical thrombectomy.
- Absolute levels of serum high-sensitivity troponin-T levels measured before the start of the first transcutaneous autonomic neuromodulation and at the end of the second transcutaneous autonomic neuromodulation.

[figure not shown]

\* please see Appendix A for details on the assessment of primary and secondary outcomes

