#### 14.6 Procedure(s) to account for missing or spurious data

As the primary outcome uses routinely captured data stored by Barts Health EPR, there is minimal risk of missing blood pressure-related data. Heart rate data will be captured by dedicated Holter monitors provide by the Chief Investigator. Any missing data will not be inputed. Sensitivity analyses to assess the robustness of study results if there are missing primary outcome data will be undertaken. This pilot study will assess data completeness to inform decisions about missing data for a future main trial. Analysis will use all participants with available endpoint data. The level of missing data will be tabulated for each outcome, presenting the number of subjects with a data record and number with missing data, separately by trial arm. Each endpoint will be analysed on a complete case basis. For continuous variables, distributional assumptions will be hard to assess with the small sample size for this pilot study. However, if any continuous endpoint variables appear to seriously violate distributional assumptions or very extreme outliers observed, then non-parametric alternative approaches to analysis will be undertaken in such cases.

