# Diastolic blood pressure variability from blood pressure measured in each patient during the first 24 hours from the start of mechanical thrombectomy.

This will be collected from routine diastolic pressure measurements as part of standard care from the start of mechanical thrombectomy for 24 hours. There will be no stipulations on the number of measurements taken. This data will be documented in the patient medical records. The data will be reported as standard deviation, average real variability, successive variation and residual standard deviation.PMID: 31813361

Heart rate variability measured during each period of transcutaneous autonomic neuromodulation. In addition to routine care all patients will wear a Holter monitor during each of the two intervention periods (for further details please see section 6.7). Heart rate variability will be derived from standard parameters using Kubios software.

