	 Exclusion criteria participation in a trial exploring similar biological mechanism; previous enrolment; anatomical contraindication (local ear abnormalities); pregnancy.
Interventions	Active stimulation bilateral active transauricular nerve stimulation for the duration of the mechanical thrombectomy procedure (AffeX-CT/001 investigational device). The intervention will be repeated for 1h the morning following the mechanical thrombectomy
	Sham stimulation bilateral sham transauricular nerve stimulation for the duration of the mechanical thrombectomy procedure (AffeX-CT/001 investigational device). The intervention will be repeated for 1h the morning following the mechanical thrombectomy
Primary outcome measure	The primary outcome is Blood pressure variability [Time Frame: 0-24h after mechanical thrombectomy], as calculated from the coefficient of variation of systolic blood pressure

3. Outcome measures

Primary outcome measure

The primary outcome is Blood pressure variability [Time Frame: 0-24h after mechanical thrombectomy], as reflected by the coefficient of variation of systolic blood pressure.

Secondary outcome measures

- 1. Systolic and diastolic blood pressure variability in the first 24h after mechanical thrombectomy [Time Frame: 0-24h after mechanical thrombectomy]: systolic and diastolic blood pressure mean, standard deviation, and coefficient of variation.
- 2. Heart rate variability [Time Frame: 0-24h after mechanical thrombectomy]: time and frequency domain measures of autonomic cardiac modulation.
- 3. NIH Stroke Scale (NIHSS) [Time Frame: recorded before, at 24h after mechanical thrombectomy]
- 4. Organ dysfunction [Time Frame: First seven days after mechanical thrombectomy.] defined as clinical need for intravenous pharmacological support for blood pressure [pressors or intravenous antihypertensive medication]; arrythmias; myocardial injury [high sensitivity troponin]; hospital-acquired infection.

Exposure variables

The exposure is bilateral active or sham transauricular nerve stimulation for the duration of the mechanical thrombectomy procedure (AffeX-CT/001 investigational device), an intervention that is be repeated for 1h the morning following the mechanical thrombectomy (provided the patient remains in Royal London Hospital).

Sample size and randomisation

Sample size calculation

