 BPV formulae are provided in supplementary data. These measures take into account the distribution and linear trends of BP in an effort to reduce the dependency of BPV on mean BP level.
- 2. Autonomic cardiac modulation in the first 24h after mechanical thrombectomy (Holter monitoring).
- 3. Neurological recovery will be reported by recording serial NIH Stroke Scale (NIHSS) scores, an FDA-approved primary outcome measure for stroke in early phase II trials before and 24h after mechanical thrombectomy.[8]

Exploratory objectives

Biomarkers for risk of infection (whole blood leukocyte transcriptomic changes after incubation at 37°C with sterile saline or 100ng/ml lipopolysaccharide for 4h), infections within 7 days of MT and myocardial injury (high-sensitivity troponin) will also be quantified. Cardiac injury will be assessed by measuring high-sensitivity troponin T on admission and 24h after MT.

Sensitivity analysis

For patients discharged before the repeat stimulation intervention or repatriated to referring centres before the repeat intervention, we will undertake a sensitivity analysis. The primary analysis will be repeated once assuming that all patients in the continue group with missing outcomes did not have BPV >20. The analysis will then be repeated again with the opposite assumptions. This will then give the absolute range of how much the results could change if the data were complete. This will also assess the robustness of our analysis of the primary outcome under the assumption that data is missing-not-at-random (MNAR).

5. Other analyses, data summaries and graphs

Clinical management

Clinical management for the treatment allocation will be summarised but not subjected to statistical testing. Numbers (%) and means (SD) or medians (IQR) will be provided separately for each principal exposure group:

- Thrombectomy technique
- General Anaesthesia/ Sedation
- Endotracheal tube inserted?
- Did the patient have any arrhythmias
- Intraoperative hypotension
- Planned level of care.

Process measures

Summary measures will be presented separately for each treatment allocation. All patients with recorded data will be included in the summary. Formal statistical analysis will not be performed. Patient status at follow up (alive/dead; home/hospital) seven days after MT will be presented as number (%).

Safety analyses

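### If session is the repeat factor, complete-case repeated measures ANOVA for heart rate variability drops the first-session recording of every patient who misses the second session

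*Protocol*

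**What the plan says.** **Two recordings per patient.** Protocol section 2.3.2 defines the endpoint as "Heart rate variability measured during each period of transcutaneous autonomic neuromodulation". Protocol Appendix A says "all patients will wear a Holter monitor during each of the two intervention periods". The sessions are the thrombectomy itself and about one hour the next morning (Protocol 6.7 and 10.10).

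**The method.** Protocol 14.4: "Blood pressure and heart rate variability measures will be analysed by repeated measures ANOVA", with significance set at p<0.05. The same section then lists HRV among outcomes that are reported without a test. The SAP names no model for HRV. Its Table 5 has one mean (SD) per arm and one p-value per measure, with no split by session.

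**Missing outcomes.** Protocol 14.6 contains three statements: "Any missing data will not be inputed", "Analysis will use all participants with available endpoint data" and "Each endpoint will be analysed on a complete case basis". Protocol 14.2 defines the intention-to-treat population by available data. The SAP's general analysis principles include every randomised patient for whom an outcome was recorded.

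**Who misses session 2.** In the SAP's exposure variables paragraph the repeat session is given "provided the patient remains in Royal London Hospital". The SAP's sensitivity analysis paragraph opens "For patients discharged before the repeat stimulation intervention or repatriated to referring centres". It then repeats the primary blood pressure analysis only. Dummy Table 2 includes repatriation as a planned level of care for the first night.

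**The concern.** A repeated measures ANOVA restricted to complete cases uses a patient only if every level of the within-patient factor was observed. HRV has two possible values per patient, and the second depends on the patient still being at the site. Read together, the protocol's method and its missing-data rule would remove a patient's thrombectomy-session recording because the next morning's recording does not exist.

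Two things are at stake. The first is precision: usable first-session data are lost in a trial of 36. The second is the population: the first-session comparison would be limited to patients still on site the next morning, a condition that arises after randomisation, although both documents undertake to use all available or recorded data. The one safeguard written for early leavers does not reach HRV.

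**Working it through.** **1. The plan's own figure.** The documents give no figure for HRV or for the share missing session 2. The only related figure is the total of 36. Inputs from the SAP: coefficient of variation 15 versus 10, SD 4, 90% power, 5% level, two-sided p-values, 5% non-compliance in each group. Diluted difference: 5 × (1 − 0.05 − 0.05) = 4.5. A two-sample t test then needs 18 per arm, or 36 in total, with 90.6% power. The 36 reproduces. It belongs to the primary outcome and serves here only as the number randomised.

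**2. Recordings lost.** Assumptions: all 36 have a session 1 recording, losses fall evenly on the arms, and a share m misses session 2. Patients kept: k = 36 × (1 − m), rounded. Recordings available: 36 + k. Recordings used under complete case: 2k.

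**3. Standard error of the session 1 comparison.** With equal arms and n patients in total, SE = σ√(4/n), so complete-case analysis inflates it by √(36/k).

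| Assumed share missing session 2 | Session 1 recordings dropped | Patients kept (k) | Recordings used / available | √(36/k) |
|---|---|---|---|---|
| 5% | 2 | 34 | 68 / 70 | 1.03 |
| 10% | 4 | 32 | 64 / 68 | 1.06 |
| 20% | 7 | 29 | 58 / 65 | 1.11 |
| 30% | 11 | 25 | 50 / 61 | 1.20 |
| 40% | 14 | 22 | 44 / 58 | 1.28 |

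A mixed model with arm, session and their interaction keeps all 36 at session 1, so its factor is 1.

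**4. If one effect common to both sessions is estimated.** Let ρ be the within-patient correlation (assumed 0.3 to 0.7). A patient with both recordings carries information 2/(1+ρ) relative to 1 for a single recording. Efficiency of complete case against all recordings is (k/36)·I ÷ [(k/36)·I + (36−k)/36], with I = 2/(1+ρ). Example at 20% missing and ρ = 0.5: I = 1.333; (29/36) × 1.333 = 1.074; 7/36 = 0.194; 1.074/1.268 = 0.85. Across ρ from 0.3 to 0.7 the efficiency is 0.93 to 0.90 at 10% missing, 0.86 to 0.83 at 20%, and 0.78 to 0.73 at 30%.

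**5. Could bias arise?** This was simulated with no true effect. If leaving early is unrelated to HRV, the complete-case session 1 difference is unbiased (average error at most 0.01 SD). If leaving depends on session 1 HRV in the active arm only (log odds 1 per SD), the bias is about −0.12, −0.20 and −0.28 SD at baseline missing rates of 10%, 20% and 30%. Using all session 1 recordings removes it. The second scenario is deliberately one-sided, and nothing in the documents says it will occur.

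**The case against.** The strongest reply is that the loss is inferred. No sentence names session as the within-patient factor, and none says a patient without session 2 leaves the session 1 comparison. Protocol 14.4 applies the method used for the primary endpoint, which has a single value per patient, so the term may be used loosely. The complete-case rule is stated per endpoint, and if each stimulation period counts as its own endpoint, every session 1 recording is kept. The available-data statements point the same way. If the line in 14.4 that leaves HRV untested governs, no ANOVA is run at all.

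Much of this stands, and the point is therefore conditional. It does not clear the plan. Neither document says what happens to a patient with one of two recordings. The explicit rule is complete case, and the SAP supplies no other HRV model. The SAP also promises an estimate, confidence interval and p-value for each secondary outcome, and Table 5 has a p-value column. Some software will fit an unbalanced ANOVA, but that would no longer follow the complete-case rule.

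A reader might also infer more than the documents support:

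- **That the HRV result will be biased.** No reasons for early departure are given, and transfer for bed reasons need not relate to HRV. Repatriation in Table 2 is a planned level of care, which Protocol 6.6 collects at baseline. Care providers are described as blinded, and no cause of departure differing by arm is offered.
- **That the plan plainly breaks intention to treat.** Protocol 14.2 defines that population by available data. What exists is a conflict between statements.
- **That session 1 is the main exposure.** It is typically longer, but Protocol 6.7 describes one intervention given at two time points.

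**Conclusion.** The point holds in conditional form. If session is the repeat factor, the protocol's method and missing-data rule together discard valid first-session HRV recordings from a group the SAP expects, against the documents' own commitments on available data and with no HRV safeguard. The cost in precision is modest: about 6% to 20% on the session 1 standard error for 10% to 30% missing. Those shares are assumptions, as are complete session 1 data and even losses between arms. Bias is possible but not shown. HRV is secondary, so the primary outcome, its sample size and its power are not affected. The change is worth making because it is nearly free and closes an open choice before unblinded data are seen.

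**What to change.** In the SAP:

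- Replace repeated measures ANOVA on complete cases for HRV with a linear mixed model: arm, session and arm-by-session as fixed effects, with a within-patient covariance, fitted to all available recordings.
- Lay out Table 5 by session, giving the arm difference, its confidence interval and the number analysed in each arm.
- Reconcile the two statements in Protocol 14.4 on whether HRV is tested, and align the SAP text and Table 5 with the answer.

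A small-sample degrees-of-freedom correction and a log scale for skewed measures are optional; neither addresses the lost recordings. The session 2 contrast from this model assumes that leaving early depends only on arm and observed session 1 HRV, and the SAP should say so. When session 1 is complete, its contrast does not need that assumption.

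The cost is SAP wording and a longer Table 5. No new data and no change to conduct are needed.
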